1. Obtaining Specimens: Preterm infants admitted to the NICU will be screened for inclusion. Each medical record will be reviewed to confirm that the standard hospital consent form was signed on admission and that there were no exclusions indicated for the collection of stool for research purposes. A subject ID number will be assigned. Stool samples identified only by subject ID number will be collected and processed to determine whether they contain *Candida* species by standard laboratory methods in the [name] research laboratory. Because colonization with *Candida* may develop over time, we will collect stool samples from eligible patients weekly throughout their hospital stay. Parent(s) of colonized infants will be approached for informed consent. Once consent is obtained, infants will be randomized into control and supplementation groups. After baseline sample collection, infants in the supplementation group will receive 0.5 ml/oz additional MCT oil (4 kcal/oz) as a nutritional supplement for 21 days or until hospital discharge. Sample collection from enrolled infants will include a stool sample and 0.5 ml of maternal breast milk obtained from a bottle provided to the patient's room. Samples will be collected three times during the study period: before supplementation is started, 1 week after supplementation is started, and at the conclusion of the supplementation period.. The following information will be extracted from the medical record of consented infants: gestational age, birth weight, day of life, gender, admitting diagnosis, prenatal infection screening labs, method of delivery, antibiotic use (duration and drug class), corticosteroid use, presence of central lines, amount and types of feeds (breast milk only, breast milk and formula, formula only; formula brand; type and amount of fortifiers and other nutritional supplements) and feeding modality (breast, bottle, NG, G-tube) will be recorded. If any infant subsequently develops an invasive fungal infection or oral thrush, that will also be noted. All information extraction will conform to HIPAA and institutional standards for protected health information.

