2. Data Analysis: Stool samples from preterm infants admitted to the ICU will be processed by standard laboratory methods in the [name] research laboratory to determine whether they contain *Candida* species. The presence and concentration of organisms will be recorded. Once infants are enrolled, stool samples and breast milk will be collected and stored for later testing at Tufts University. The presence and concentration of microbes in stool samples will be quantified, and the fatty acid content of breast milk samples will be analyzed. All identifiers will be removed from all samples collected for this study; they will be identified only by subject study ID number. No PHI will be provided to Tufts. Laboratory data generated from these studies will be maintained independent from any patient identifying information. Patient identifiers will be maintained in coded fashion secured in [name] office at Women & Infants Hospital. This office is in a building distinct from that of the laboratory.

Candida MCT

Microbiological Methods: Stool samples will be weighed and suspended in 10 ml of sterile saline. Serial dilutions will be cultured on YPD agar media (1% yeast extract, 2% peptone, 2% dextrose, 2% agar) containing 100 µg/mL streptomycin and 50 µg/mL ampicillin to inhibit bacterial growth and to allow quantification of the yeast content per gram of stool. Colonies will be evaluated by light microscopy to confirm that they are comprised of yeast. Yeast will be speciated using the FDA-approved Vitek-2 system.

3. Safety Assessments: Because MCT oil is already a component of infant formulas and breast milk, and because recommended dietary intakes will not be exceeded, there are no specific procedures, laboratory evaluations, or measures required to monitor infants receiving the supplement. Routine clinical care and assessments will be undertaken, with the option to discontinue the supplement in the unlikely event that there is any clinical suspicion of intolerance. In particular, enrolled patients receiving supplemental MCT oil will be monitored for the following signs/symptoms:

1. Feeding intolerance – defined as any clinical event related to feeding (gastric aspirates, emesis, abdominal distension) that results in a reduction or withholding of enteral feedings for a period of 24 hours or more.
2. Diarrhea
3. Necrotizing enterocolitis
4. Poor weight gain
5. Excessive weight gain

Adverse event

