An adverse event is any untoward medical occurrence in a patient or trial subject administered a pharmaceutical product; the event does not necessarily have a causal relationship with the treatment or usage. Adverse events include the following:

- Abnormal test findings, as specified below.
- Clinically significant signs and symptoms.
- Changes in physical examination findings.
- Progression/worsening of underlying disease.

Abnormal test findings

An abnormal test finding, e.g., abnormal laboratory analysis results or vital signs, should be recorded as an adverse event in any of the following situations:

- The investigator considers the test result to be clinically significant.
- The test is associated with accompanying symptoms. Note, that the symptom, not the test result, should be recorded as an adverse event.
- The test result leads to a medical/surgical intervention including withdrawal of investigational product or discontinuation from the study. Repeat/confirmatory testing is not considered a medical intervention.

Serious adverse event (SAE)

An adverse event that meets one or more of the following criteria/outcomes is classified as serious:

- Results in death.
- Is life-threatening (i.e., at immediate risk of death).

Candida MCT

- Requires prolongation of hospitalization.
- Results in persistent or significant disability/incapacity.
- Other medically important adverse event that may not result in death, be life threatening, or require hospitalization may be considered serious when, based upon appropriate medical judgment, they may jeopardize the patient or may require medical or surgical intervention to prevent one of the outcomes listed above.

Adverse Event Grading Scale

The adjectives MILD, MODERATE, or SEVERE will be used to describe the maximum severity of the adverse event. For the purpose of consistency, these intensity grades are defined as follows:

- MILD: Does not interfere with patient's usual function.
- MODERATE: Interferes to some extent with patient's usual function.
- SEVERE: Interferes significantly with patient's usual function.

Note the distinction between the gravity (seriousness) and the intensity (severity) of an adverse event. **Severe** is a measure of intensity; thus, a **severe** reaction is not necessarily a **serious** reaction. For example, a headache may be severe in intensity, but would not be classified as serious unless it met one of the criteria for serious events listed above.

Causality assessment

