For each adverse event, a causality assessment will be made to determine if there is a reasonable possibility that the investigational product caused the adverse event. The adverse event is assessed using the following classification and criteria:

Not related: This relationship suggests that there is no association between the investigational product and the reported event.

Unlikely: This relationship suggests that the temporal sequence of the clinical event, including a laboratory test abnormality, with investigational product administration makes a causal relationship improbable, and that other drugs or underlying diseases provide plausible explanations.

Possible: This relationship suggests that treatment with the investigational product caused or contributed to the adverse event, i.e., the event follows a reasonable temporal sequence from the time of drug administration or follows a known response pattern to the investigational product, but could also have been produced by other factors.

Probable: This relationship suggests that a reasonable temporal sequence of the event with investigational product administration exists and, based upon the known pharmacological action of the drug, known or previously reported adverse reactions to the drug or class of drugs, or judgment based on the investigator's clinical experience, the association of the event with the investigational product seems likely.

Definite: This relationship suggests that a definite causal relationship exists between investigational product administration and the adverse event, and other conditions (concurrent illness, progression/expression of disease state, or concurrent medication reaction) do not appear to explain the event.

“**Not related**” and “**unlikely**” will be included in the category “**unrelated**” (i.e., not having a reasonable suspected causal relationship to the investigational product).

“**Possible**”, “**probable**” and “**definite**” will be included in the category “**related**” (i.e., having a reasonable causal relationship to the investigational product).

IV. Risk/Benefit Assessment

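### The five targeted safety signs are monitored only in infants receiving MCT oil, so events in that group have no equally ascertained background in the randomized controls

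*Protocol*

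**What the plan says.** Under section III, item 1 (Obtaining Specimens), once parents consent, "infants will be randomized into control and supplementation groups". The supplementation group gets MCT oil for 21 days or until discharge.

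Item 1 also sets out a chart extraction that applies to both groups: "The following information will be extracted from the medical record of consented infants". The list includes birth weight, admitting diagnosis, antibiotic use and "amount and types of feeds". It adds that invasive fungal infection or thrush is noted in any infant who develops it.

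Item 3 (Safety Assessments) first explains that, because MCT oil is already present in formula and breast milk and intakes stay within recommendations, "there are no specific procedures, laboratory evaluations, or measures required to monitor infants receiving the supplement". It relies on routine care, with the option to stop the oil if intolerance is suspected. It then names a specific list: "enrolled patients receiving supplemental MCT oil will be monitored for the following signs/symptoms". The five signs are feeding intolerance (defined through feeds reduced or withheld for at least 24 hours), diarrhea, necrotizing enterocolitis (NEC), poor weight gain and excessive weight gain.

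The adverse event definition that follows covers "any untoward medical occurrence in a patient or trial subject administered a pharmaceutical product". The causality scale is applied to each adverse event. Its middle grade asks, among other things, whether "the event follows a reasonable temporal sequence from the time of drug administration", and allows that it fits the product "but could also have been produced by other factors".

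**The concern.** Controls are enrolled and randomized but receive no supplemental oil, so the monitoring sentence read literally leaves them out. The protocol picks five signs worth watching and then watches for them in one randomized group only.

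If several MCT infants had feeds withheld or developed NEC, someone would have to judge whether the oil was responsible. By clinical judgement, preterm infants have such events without MCT oil; the protocol gives no background rates. A control group in the same unit over the same weeks is the natural reference, and this study already has one. Without matching records, that reference is not collected.

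Weight gain shows the point well. The oil adds 4 kcal/oz, so a change in growth is plausible, yet there is no instruction to record weight gain in controls against which to read poor or excessive gain. The protocol also says its data will inform a later interventional trial. That trial's stated question is colonization, so a two-group safety record would be useful to it but is not promised.

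**Working it through.** The protocol states no safety event rates, and none are needed. The check is to read every place that says who is monitored, what is extracted and what counts as an adverse event, and to ask whether any of them brings the five signs to controls.

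**1. Monitoring instruction (Safety Assessments).** It names infants receiving the oil. Signs assigned: MCT group 5 of 5, controls 0 of 5.

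**2. Routine-care sentence (Safety Assessments).** It names no group, so controls are presumably observed clinically. It does not say that the five signs are recorded for the study in controls.

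**3. Common extraction list (Obtaining Specimens).** It covers all consented infants:

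| Sign | On the common list? |
|---|---|
| Feeding intolerance | Partly: feed amounts can show a reduction, but the triggering event is not listed |
| Diarrhea | No |
| NEC | No: only the admitting diagnosis is listed; feeds and antibiotic use may leave an indirect trace |
| Poor weight gain | No: birth weight only |
| Excessive weight gain | No: birth weight only |

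That is 1 partly covered and 4 not listed (1 + 4 = 5). The list is the same for both groups, so serial weights are missing from it for MCT infants too. What differs between groups is the monitoring instruction in step 1.

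**4. Outcomes noted in any infant (Obtaining Specimens).** These are invasive fungal infection and thrush. Neither is among the five. Here the protocol uses wording that reaches every infant; for the five signs it does not.

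**5. Adverse event definition.** It is tied to a subject who was given a product, so it does not plainly reach an unsupplemented control.

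**6. Causality grading.** It weighs timing after administration against other explanations. The protocol collects no matching record of how often those other explanations produce the same signs in unsupplemented infants.

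None of steps 2 to 6 fills the gap left by step 1.

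**The case against.** The best defence is that the list is a tolerability safeguard. It follows directly on the option to stop the supplement, and controls have nothing to stop. Both specific aims concern colonization. The protocol also gives reasons for light monitoring here and in section IV: the oil is already in infant feeds, is in routine use, and stays within recommended intake. This stands in part. It explains why no new procedures are added and why safety is a minor matter in this study. It does not explain recording the signs in one randomized group when both groups' charts are already being opened.

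A second defence is that causality is graded infant by infant, which does not require a control count, and that other grades on the scale already allow for underlying disease, other drugs and concurrent illness. That is correct. A control record would help those judgements; the scale does not depend on it.

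Third, controls are inpatients in the same unit, so NEC, weights and feed interruptions are probably in their charts. A reader might infer that this information is lost in controls. The protocol does not support that; it shows only that there is no instruction to record it or to apply the same definitions.

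A reader might also infer that the safety results will be biased, or that serial weights were left out for controls alone. Neither holds. No between-group safety analysis is stated, and the extraction list omits serial weights for everyone.

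**Conclusion.** The point holds as a matter of unequal ascertainment written into the protocol: five of five targeted signs are assigned to the MCT group and none to controls, with one of the five partly recoverable from the shared extraction list. Events seen under MCT oil would have no equally ascertained concurrent background.

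Its weight is low. Safety is not a stated aim, no stated result is biased, and no size or direction of bias can be given from the document. The reading takes the monitoring sentence literally; if the sponsor always meant to include controls, the change only makes that explicit. Whether monitoring continues after an infant stops the oil early is unclear from the wording, but the adverse event definition has no time limit and probably still captures such events, so nothing is claimed there. Consider it as a cheap improvement.

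**What to change.** Two changes in section III:

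- **Item 3, Safety Assessments.** Replace the monitoring sentence with: *All randomized infants, in both groups, will be followed through routine care and chart review for the five signs below, using the same definitions, from randomization through day 21 of supplementation (the matching day in controls) or discharge, whichever is first, whether or not the supplement is stopped. Signs recorded in controls will not be graded for causality.*
- **Item 1, Obtaining Specimens.** Add the five signs with dates, and serial weights, to the extraction list for all consented infants.

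Leave the adverse event definition and the causality scale as they are for supplemented infants. Widening the definition to all randomized infants would be a mistake: every adverse event must have a causality assessment, so control events would have to be graded against a product those infants never received, and the workload would grow well beyond five signs. The option to stop the supplement is unchanged.

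The cost is modest extra chart review in both groups, in records already being extracted. Some events unrelated to the supplement will be recorded. No new visits, samples or procedures are needed.
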